### *Procedures*

Those patients who were eligible according to inclusion and exclusion criteria described above and agreed to participate in this study signed an informed consent sheet. All data were originally acquired from participants entering this single research center clinical trial to investigate the efficacy of tDCS treatment.

After global physical and clinical examination subjects were randomly assigned to one of the two groups (sham- and real tDCS) in a 1:1 ratio using a computer-generated block randomization sequence that was kept with the unblinded study coordinator (not involved in the recruitment). The co-investigator conducting treatments was only given a list of 5-number blinding codes to be loaded to the DC-stimulator before each session of brain stimulation. The device is previously settled with specific settings for the study.

After patients had been admitted to the hospitals, they were maintained under regular treatment for 30 days in average or until they had reached a global clinical stabilization, to have them started in the sham- or real tDCS treatments. The brain stimulation application was then performed in one 20-min session a day, every other day, including weekends, up to a total of 10

sessions, always in the afternoon period, in the following five weeks and they were followed-up after the end of the stimulation treatment for up to 60 days after their discharge from the hospitals.

Craving was measured once a week over five weeks (once before the beginning of the stimulation sessions, three times over the stimulation sessions and once more after the end of stimulation sessions) with a total of five time-points measurements. Relapses were collected after discharge from the hospital up to 60 days after intervention.

Participants and experimenters were blinded for brain stimulation assignments from the beginning of the study protocol up to the end of the 60-days follow-up after the end of sham- or real tDCS treatment, resulting in a double-blind experimental design.

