### *Participants*

All subjects were informed about the purposes of the experiment by the principal investigator and signed a written consent before entering the study.

Thirty-five patients, 29 men and 6 women, who met DSM V criteria for cocaine (crack) use disorder were recruited between June of 2015 and April of 2018 from three specialized clinics for drug use disorder treatment (one public and two private hospitals) from Espírito Santo State, Brazil. They all received standard treatment given by the clinics, consisting of psychosocial approaches – conducted by a professional team of psychologists, nurses, social workers and physicians – sometimes combined with adjunctive pharmacotherapy including benzodiazepines, B-complex vitamins, disulfiram and, if necessary, antidepressants, anxiolytics, antipsychotics, antihypertensive and gastric medication. It must be mentioned that in the public hospital, from where half of the patients was recruited, they were not allowed to have any medication, except non-opioid pain relievers when absolutely necessary, after they had been admitted to the hospital. Therefore, half of the patients were free of medication during the sham- or DC-stimulation. From the other half patients coming from the two private clinics, few of them were medicated (antipsychotics, antidepressants or mood stabilizers) during brain stimulation procedures.

There were two dropouts in the sham-tDCS group that were excluded after randomization. One patient escaped from the treatment facility and the other had to be discontinued because of precocious discharge from the clinic for misconduct.

The inclusion criteria for this study were: (1) male and female patients over the age of 18 years; (2) met criteria for crack-cocaine use disorder according to the ICD-10 Classification of Mental and Behavioral Disorders and the Diagnostic and Statistical Manual of Mental Disorders, fifth edition, as

determined by clinical evaluation; (3) in stable clinical condition with no need for emergency care; (4) able to read, write, and speak Portuguese; and (5) no severe withdrawal signs or symptoms at baseline.

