### *Statistical Analysis*

We powered the study for a medium effect size based on the results of our previous study (Batista et al., 2015) in which the effect size (partial  $\eta^2$ ) for the main within-subject factor in the respective two-way ANOVA with repeated measures was 0.10384 when comparing craving scores once before, twice during and once after 5-sessions of tDCS (four time-points). The tDCS electrode montage was identical in the studies, and patient populations of crack-cocaine users were similar. We used the correction for SPSS input into the G\*Power 3.1.9.2. With this effect size, for the two-way mixed model ANOVA of the present study with the within factor craving measurements, the

between-subject factor tDCS condition, the dependent variable craving score, and craving measurements x condition interaction as the primary outcome parameter, with a power of 80%, and a two-sided probability of a type I error of 5%, the resulting minimum sample size was 30 participants. To account for waiving or dropouts, which were expected to be very common in this condition, we increased the estimated sample size to approximately 10%, resulting in 33 subjects in total (approximately 16 to 17 subjects in each group).

Most of data (age, patterns of crack-cocaine use, 5-items OCCS) were normally distributed according to the D'Agostino & Pearson normality test, thus they were analyzed by parametric tests. Between-group (sham- and real tDCS) comparisons were conducted by unpaired *Student's t*-tests. For all other non-parametric data (gender, schooling, employment, marital state and tobacco use), Chi-square or Fisher tests were used to compare sham and real tDCS groups.

Besides the two-way ANOVA with repeated measures followed by Bonferroni-corrected t-tests, linear regression analyses were done over craving scores obtained along the 4-week treatment (five time-points measurements) for both groups. Additional comparisons between initial and final OCDS scores were done by paired t-tests for each group, and differences between final and initial scores were compared between sham-tDCS and real tDCS groups with unpaired t-test. Effect sizes were calculated using Cohen's *d* and corrected by Hedges's  $g_s$  for unpaired and Hedges'  $g_{av}$  for paired t-tests (Lakens, 2013).

A two-tailed p-value of 0.05 or less was considered to indicate statistical significance. SPSS Statistics Base 24.0 (SPSS Inc, USA) and GraphPad Prism

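### Hospital type, which determines the medication policy, is in neither the described randomisation nor the craving analysis; the expected cost is lost precision and an uncorrected chance imbalance, not systematic bias

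*Combined protocol and SAP*

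**What the plan says.** **Recruitment and background care (Participants).** Patients came from one public and two private hospitals. On the public one: "in the public hospital, from where half of the patients was recruited, they were not allowed to have any medication" after admission, with an exception for non-opioid pain relievers. The section concludes that "half of the patients were free of medication during the sham- or DC-stimulation". Of the private half it says that "few of them were medicated (antipsychotics, antidepressants or mood stabilizers) during brain stimulation procedures", without a count. Thirty-five patients were recruited. It adds: "There were two dropouts in the sham-tDCS group that were excluded after randomization", which leaves 33.

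**Allocation (Procedures).** Patients were assigned "in a 1:1 ratio using a computer-generated block randomization sequence that was kept with the unblinded study coordinator". No block size and no stratification factor is given. The same section calls the trial single-centre.

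**Analysis (Statistical Analysis).** The primary test is the time × condition interaction in a two-way repeated-measures ANOVA, with tDCS condition as the only between-subject factor. The t-tests and linear regressions add no further factor. The variables listed for comparison between arms are age, patterns of use, craving score, gender, schooling, employment, marital state and tobacco use. Hospital and medication are not among them.

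**The concern.** The protocol itself singles out a difference in background care between hospital types, then uses it nowhere in the described allocation or analysis. Two consequences follow in a trial of 33 analysed patients.

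- If craving takes a different course in the two hospital types, that variation goes into the error term of the primary test.
- If the arms happen to hold different shares of public-hospital patients, part of the hospital difference is carried into the realised sham-versus-real contrast and nothing in the model removes it. Without a table by arm, a reader cannot tell whether this happened.

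The planned size leaves little spare precision: the minimum of 30 was set for 80% power.

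**Working it through.** **1. The plan's own figure.** Inputs from Statistical Analysis: partial η² = 0.10384, 80% power, two-sided 5%, two groups. With five measurements, sphericity and the SPSS effect-size option, f² = 0.10384/(1 − 0.10384) = 0.1159, λ = f²(N − 2)(5 − 1), df = 4 and 4(N − 2). At N = 30, λ = 0.1159 × 28 × 4 = 12.98 and power is 81.8%. The smallest N is 29, or 30 with equal arms, so the stated 30 is reproduced. A hospital term with its time interaction replaces N − 2 by N − 3. N = 30 then behaves like N = 29 in the planned model, still at 80%. The required size does not change.

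**2. Chance imbalance.** Assume 33 analysed, 17 real and 16 sham, 17 from the public hospital, and allocation unrelated to hospital. The documents say only that half were public and do not give the realised arm sizes. The number of public patients in the real arm is then hypergeometric(33, 17, 17).

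| Difference in public share | 33 analysed (17/16) | 35 randomised (17/18) |
|---|---|---|
| at least 20 points | 0.303 | 0.181 |
| at least 25 points | 0.169 | 0.181 |
| at least 30 points | 0.084 | 0.094 |

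With 16 public patients among the 33, the first column is unchanged. The 20-point row is unstable because counts are discrete. With 35 patients, the split 10/17 against 7/18 is 58.8% − 38.9% = 19.9 points and just misses the cut. The 25-point row, about 17–18%, is the one to rely on.

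**3. Shift in the realised contrast.** Shift = hospital effect × imbalance. At 25 points it is 0.25 × 0.5 = 0.125 SD for a hospital effect of 0.5 SD, and 0.25 × 1 = 0.25 SD for 1 SD. The standard deviation of the treatment estimate on the change score is about 0.34 SD, so the larger shift is 0.25/0.34 ≈ 0.7 of a standard error.

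**4. Precision.** A two-level factor split half and half has variance 1/4. Ignoring it therefore gives a residual variance of 1 + δ²/4, where δ is the hospital effect on craving change in SD units. Adjusting returns the residual variance to 1 but pays for chance correlation with treatment, taken as 31/30 (residual df 33 − 2 over 33 − 3). The ratio of standard errors, adjusted to unadjusted, is √(31/30) / √(1 + δ²/4).

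| δ (assumed) | Change in standard error |
|---|---|
| 0 | +1.7% |
| 0.25 | +0.9% |
| 0.5 | −1.4% |
| 0.75 | −4.8% |
| 1 | −9.1% |

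Break-even is at δ = 2√(1/30) = 0.37 SD.

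**5. Simulation check.** Change-score comparison, 34 patients, blocks of four (assumed), true treatment effect 1 SD for power, 8,000 runs per setting.

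| δ | Unstratified, unadjusted | Unstratified, adjusted | Stratified, adjusted |
|---|---|---|---|
| 0 | 80.9% | 79.8% | 80.6% |
| 0.5 | 77.9% | 78.7% | 81.0% |
| 1 | 71.6% | 80.1% | 80.5% |

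With no treatment effect, the unstratified, unadjusted test rejected in 4.8% to 5.2% of runs, and its mean estimate was close to zero. Stratifying without adjusting made the test conservative at δ = 1 (3.2% rejections).

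**The case against.** The best reply is that little is at stake.

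- **Medication may barely differ.** If few private patients were medicated, most were in the same position as the public patients. If medication were the only route, the drug effect needed to reach break-even is 0.37 divided by the medicated share of the private half. That is 3.7 SD at 10%, 1.5 SD at 25% and 0.7 SD at 50%. These shares are assumptions, since the count is not given. This stands, and it makes the 1 SD row an upper illustration rather than an expectation. Hospital type may carry other differences, but the documents describe none that bear on craving.
- **Level differences drop out.** The primary test is an interaction with time and includes a pre-treatment score, so a stable difference in craving level between hospitals does no harm. Only a different course matters. Patients were also kept under regular treatment for about 30 days, or until stable, before stimulation. This stands.
- **Blocking may help.** If one site's patients enrolled in runs, a common block list would balance them in part. The enrolment order is not given, so this can be neither credited nor dismissed.
- **A post hoc covariate is its own problem.** Changing the primary model after data have been seen is undesirable. This stands and shapes the fix.

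A reader might go further and infer that the sham comparison is biased by design, that the arms were in fact unbalanced, or that the list was certainly unstratified. The documents support none of these. Randomisation protects the comparison on average, no split by arm is reported, and silence on strata is not proof of their absence.

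**Conclusion.** The point holds as one of precision and transparency. Hospital type is tied to medication policy, is not described as a stratum, and is missing from the craving model and the listed comparisons. An imbalance of at least 25 points has a probability of about 17–18%, given a half-and-half public/private split and near-equal arms.

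Whether it matters depends on a hospital effect on the course of craving, which the documents do not give. Adjustment costs up to about 2% in standard error below roughly 0.37 SD and gains above it, reaching about 9% at 1 SD. Over repeated randomisations the unadjusted estimate is unbiased and the type I error holds, so bias can be spoken of only as an uncorrected shift in this one sample. The two post-randomisation exclusions, both sham, may have altered the balance further in either direction. Tabulating hospital type and medication by arm is justified whatever the size of the effect.

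**What to change.** 1. Analyse craving with hospital type (public/private) and its interaction with time added to the time × condition model. The Statistical Analysis section already reports the outcome of a normality test on the craving scores, which suggests that the data had been examined. If so, label this a sensitivity analysis and present it beside the stated primary analysis.
2. Show hospital type and medication during stimulation by arm in the baseline table, for all 35 recruited and for the 33 analysed.
3. State the block size and whether the sequence was stratified. If it was, include the stratum in the model, because stratifying without adjusting makes the test conservative.
4. Separate block lists for the public hospital and the private clinics can serve only a future trial, because recruitment ended in April 2018.

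The first three items need only records that the trial should already hold. The cost is one between-patient degree of freedom and slight collinearity, about 2% in standard error if hospital is unrelated to craving change. Two levels are preferable to three, since the counts per private clinic are not given and may be small.

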### *Statistical Analysis*

We powered the study for a medium effect size based on the results of our previous study (Batista et al., 2015) in which the effect size (partial  $\eta^2$ ) for the main within-subject factor in the respective two-way ANOVA with repeated measures was 0.10384 when comparing craving scores once before, twice during and once after 5-sessions of tDCS (four time-points). The tDCS electrode montage was identical in the studies, and patient populations of crack-cocaine users were similar. We used the correction for SPSS input into the G\*Power 3.1.9.2. With this effect size, for the two-way mixed model ANOVA of the present study with the within factor craving measurements, the

between-subject factor tDCS condition, the dependent variable craving score, and craving measurements x condition interaction as the primary outcome parameter, with a power of 80%, and a two-sided probability of a type I error of 5%, the resulting minimum sample size was 30 participants. To account for waiving or dropouts, which were expected to be very common in this condition, we increased the estimated sample size to approximately 10%, resulting in 33 subjects in total (approximately 16 to 17 subjects in each group).

Most of data (age, patterns of crack-cocaine use, 5-items OCCS) were normally distributed according to the D'Agostino & Pearson normality test, thus they were analyzed by parametric tests. Between-group (sham- and real tDCS) comparisons were conducted by unpaired *Student's t*-tests. For all other non-parametric data (gender, schooling, employment, marital state and tobacco use), Chi-square or Fisher tests were used to compare sham and real tDCS groups.

Besides the two-way ANOVA with repeated measures followed by Bonferroni-corrected t-tests, linear regression analyses were done over craving scores obtained along the 4-week treatment (five time-points measurements) for both groups. Additional comparisons between initial and final OCDS scores were done by paired t-tests for each group, and differences between final and initial scores were compared between sham-tDCS and real tDCS groups with unpaired t-test. Effect sizes were calculated using Cohen's *d* and corrected by Hedges's  $g_s$  for unpaired and Hedges'  $g_{av}$  for paired t-tests (Lakens, 2013).

A two-tailed p-value of 0.05 or less was considered to indicate statistical significance. SPSS Statistics Base 24.0 (SPSS Inc, USA) and GraphPad Prism

7.0 (GraphPad Software Inc, USA) were employed for statistical analysis and graphic presentations.

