**Title:** Prefrontal Modulation by Repetitive Bilateral Transcranial Direct Current Stimulation (tDCS) in Crack-Cocaine Inpatients

**Brief Title:** Bilateral Prefrontal Modulation in Crack-Cocaine Addiction (tDCS\_CRACK)

**Institution:** Federal University of Espírito Santo

**Principal Investigator:** [name], PhD

Identifiers: NCT02091167

Unique Protocol ID: tDCS CRACK CEP\_UFES 384281

Secondary IDs: CNPq\_ 475232/2013-5

**Date:** October 23, 2018

Transcranial direct current stimulation (tDCS) is a non-invasive brain stimulation tool which has proven to be efficient in modulating brain activity (George and Aston-Jones, 2010). Previous studies already demonstrated favorable effects of tDCS compared to sham stimulation in substance use disorders and craving. Accordingly, we have demonstrated that in crack-cocaine dependent subjects, five sessions of right anode/left cathode bilateral stimulation of the dlPFC was able to significantly reduce craving both during and after treatment in the real tDCS group as compared to a sham-tDCS group (Batista et al., 2015). Thus, we hypothesized that extension of repetitive bilateral dlPFC tDCS to ten sessions would have a more pronounced effect on craving in crack-cocaine substance use disorder, considering that a successful management of craving during treatment is highly desirable to prevent dropouts and relapses.

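### The 80% power for the primary time-by-condition interaction rests on an effect size labelled as the earlier study's within-subject factor, so it is unsupported as written

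*Combined protocol and SAP*

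**What the plan says.** The sample-size paragraph under Statistical Analysis draws its effect size from the sponsor's earlier study of five sessions. It describes the value as that "for the main within-subject factor in the respective two-way ANOVA with repeated measures was 0.10384 when comparing craving scores" measured "once before, twice during and once after 5-sessions of tDCS (four time-points"). It continues "With this effect size, for the two-way mixed model ANOVA of the present study" and names the term being powered: "craving measurements x condition interaction as the primary outcome parameter, with a power of 80"%. With a 5% type I error and the SPSS option in G\*Power, it reports that "the resulting minimum sample size was 30 participants", raised to 33 for dropouts.

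The reasons given for borrowing from the earlier study are the identical electrode montage and the similar population. The present trial measures craving weekly, "with a total of five time-points measurements" (Procedures). The opening background says in words that five sessions were able to "significantly reduce craving both during and after treatment in the real tDCS group as compared to a sham-tDCS group". It gives no interaction effect size and no figure for the change on sham.

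**The concern.** In a two-arm mixed ANOVA, the within-subject (time) term tests whether the average craving profile, pooled over arms, changes. The interaction tests whether the two arms' profiles differ. If both arms improve equally, the time effect can be large while the interaction is zero. If the arms move in opposite directions, the time effect can be smaller than the interaction. A time effect therefore does not fix the interaction in either direction. The similarity of montage and population justifies the choice of study, not the choice of term.

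The interaction is the primary test. If it is non-significant, readers will take the result as coming from a trial with 80% power for that test, and the text does not establish this.

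**Working it through.** **Inputs.** From Statistical Analysis: partial eta-squared 0.10384, alpha 0.05, power 80%, SPSS convention. From Procedures: two groups at 1:1, m = 5 time points. Assumed, because not stated: sphericity (epsilon = 1).

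**Formulas.** f² = η²/(1 − η²); λ = f²(N − 2)(m − 1)ε; df1 = (m − 1)ε; df2 = (N − 2)(m − 1)ε; power from the noncentral F.

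**Step 1: reproduce the plan.** f² = 0.10384/0.89616 = 0.11587, so f = 0.3404. At N = 30, df1 = 4, df2 = 28 × 4 = 112 and λ = 0.11587 × 112 = 12.98, which gives power 0.818. N = 28 gives 0.784, so 30 is the smallest even N. N = 33 gives 0.862. The inflation also matches: 30 × 1.10 = 33. With m = 4 the smallest even N is 36, so five time points were evidently entered.

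**Step 2: can N = 30 reveal which term was used?** No. With two groups, the interaction has (2 − 1)(m − 1) = m − 1 numerator degrees of freedom, the same as the time term. The denominator is also the same, so both terms give the same N.

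**Step 3: dependence on the true interaction** (m = 5, epsilon 1).

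| Interaction partial η² (assumed) | Power, N=30 | Power, N=33 |
|---|---|---|
| 0.04 | 0.36 | 0.39 |
| 0.06 | 0.53 | 0.58 |
| 0.08 | 0.68 | 0.73 |
| 0.10 | 0.80 | 0.85 |
| 0.12 | 0.88 | 0.92 |
| 0.14 | 0.94 | 0.96 |

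The interaction detectable with 80% power is 0.100 at N = 30 and 0.091 at N = 33.

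**Step 4: if 0.10384 is the time effect.** Assume equal arms and profiles of the same shape, with active change d(t) and sham change r·d(t). The mean profile is d(1 + r)/2 and each arm's deviation from it is d(1 − r)/2 in size. Hence f²(interaction) = f² × [(1 − r)/(1 + r)]². For r = 0.10 this is 0.11587 × (0.9/1.1)² = 0.0776, or η² = 0.0720. The documents give neither r nor its sign.

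| r (assumed) | Interaction η² | Power, N=30 | Power, N=33 |
|---|---|---|---|
| −0.10 | 0.148 | 0.95 | 0.97 |
| −0.05 | 0.124 | 0.90 | 0.93 |
| 0 | 0.104 | 0.82 | 0.86 |
| 0.10 | 0.072 | 0.62 | 0.68 |
| 0.25 | 0.040 | 0.36 | 0.39 |

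Power stays at 80% for r up to about 0.010 at N = 30 and 0.037 at N = 33.

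**Step 5: how plausible are these rows?** They are not equally likely. All patients received standard treatment (Participants), which makes shared improvement possible. Against that, before stimulation "they were maintained under regular treatment for 30 days in average or until they had reached a global clinical stabilization" (Procedures), which leaves less room for it. The earlier significant benefit over sham also bears on r. If it rested on this interaction (assumption), the observed F is f²(interaction) × (N − 2) on 3 and 3(N − 2) degrees of freedom. Reaching p < 0.05 then needed an earlier N of at least 19 at r = −0.10, 26 at r = 0, 37 at r = 0.10 and 66 at r = 0.25. The documents do not give that N, so this cannot be taken further.

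**Step 6: if 0.10384 is the interaction, mislabelled.** N = 30 then stands, but on unstated conditions. At an assumed epsilon of 0.8, power is 0.748 at N = 30 and 0.796 at N = 33. With the earlier study's four time points entered and epsilon 1, it is 0.726 and 0.776.

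**The case against.** The strongest defence is that a power statement is conditional. The plan says it targets a medium effect, gives the value and names the tested term, and for an interaction of 0.10384 the answer of 30 is correct. That much stands. However, the paragraph presents the value as an empirical result of the earlier study, not as a freely assumed interaction, and that basis is what fails.

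Second, the wording is loose, and the phrase about the main within-subject factor may have been meant for the interaction. This is possible and cannot be excluded. It would still leave a wrong label in the justification of the primary test.

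Third, the background expects ten sessions to work better than five, so carrying the five-session value forward could be called cautious. That is a hypothesis without a figure. It also does not help if the value carried forward belongs to another term.

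Fourth, the practical consequence is limited. Recruitment has closed, 35 − 2 = 33 patients remain, which is the planned total, and power there is 0.862 at the stated effect. This is right, and it limits the correction to reporting.

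**Conclusion.** The concern holds. The label on the effect size and the term being powered differ, and nothing in the documents connects them, so the 80% claim for the primary interaction is unsupported as written. The calculation itself is correct for its input (0.818 at N = 30, 0.862 at N = 33, five time points, sphericity).

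True power is unknown and may be higher or lower than stated; the trial is not shown to be underpowered. The scenario figures rest on assumed interaction sizes or, for the sham-ratio table, on same-shaped profiles and an assumed r. They show how sensitive the claim is, not what the power was. The point should be corrected before the power statement is relied on to interpret a null result.

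**What to change.** State which term of the earlier ANOVA 0.10384 belongs to.

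- **If it is the time effect:** restate power at N = 33 using the time-by-condition partial eta-squared from that same ANOVA. If that value cannot be used, withdraw the 80% claim and report the detectable interaction: partial eta-squared about 0.091 for 80% power at N = 33 under sphericity.
- **If it is the interaction:** correct the label. Add that N = 30 assumes sphericity and carries a four-time-point value unchanged to five time points.

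The cost is one value looked up in the sponsor's own earlier analysis and one reworded paragraph. Recruitment ended in April 2018 (Participants), so the sample size, primary test and conduct do not change and no patients are added. The price to the sponsor is that the stated power may become less favourable or have to be withdrawn.

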### *Craving assessment*

Craving was scored through a brief scale composed of five items (1, 2, 4, 5, and 13) of the Obsessive-Compulsive Cocaine Use Scale, also known as the Obsessive-Compulsive Cocaine Scale (OCCS), which are based on the Obsessive-Compulsive Drinking Scale (Anton et al., 1995;Anton et al., 1996;Anton, 2000), as proposed by Hormes et al. (Hormes et al., 2012) and

Vorspan et al. (Vorspan et al., 2012). These five-item scales assess craving in a narrow sense according to De Wildt et al. (de Wildt et al., 2005).

Through this brief scale it is possible to quantify thoughts and feelings (obsessions), and behavioral intentions (de Wildt et al., 2005), answered on a scale ranging from 0 to 4, resulting in a total score between 0 and 20. Patients are questioned on how much of the time (total per day), when the drug is not used, is occupied by thoughts, ideas, desires, or impulses related to crack-cocaine and its effects; how frequently these thoughts, ideas, desires, or impulses related to crack-cocaine and its effects occur; how much distress or disturbance these ideas, thoughts, impulses or desire related to crack-cocaine use cause when the person is under withdrawal; how much effort they have to make to resist these thoughts, ideas, desires, or impulses, or how much energy they have to spend to think of something else when they enter the mind under withdrawal; and finally ask about their drive to use crack-cocaine.

The OCCS was applied in the week before the beginning of the real or sham-tDCS treatment, during the treatment (second, third and fourth weeks) and in the week after the end of the brain stimulation application, resulting in five time-points measurements.

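### The primary ANOVA treats the pre-stimulation craving score as an outcome level rather than a covariate, which costs power on the primary interaction test

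*Combined protocol and SAP*

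**What the plan says.** The Statistical Analysis section specifies a two-way mixed ANOVA with craving measurement as the within factor and tDCS condition as the between factor. It names the "craving measurements x condition interaction as the primary outcome parameter".

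Two sections show which measurements these are. Craving assessment says "The OCCS was applied in the week before the beginning of the real or sham-tDCS treatment", with further scores during and after treatment, five in all. Procedures describes the schedule as "once before the beginning of the stimulation sessions, three times over the stimulation sessions and once more after the end of stimulation sessions". So the first of the five levels precedes any stimulation.

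For sample size, the plan takes the partial eta-squared of an earlier study, where the value for the "main within-subject factor in the respective two-way ANOVA with repeated measures was 0.10384". It enters this in G*Power with the SPSS option, at 80% power and 5% two-sided alpha. It reports that "the resulting minimum sample size was 30 participants", raised to 33 for dropout.

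No section mentions a baseline covariate, an ANCOVA or a constraint on the baseline means. The only other between-arm use of baseline is the additional unpaired t-test on final minus initial score, which is not the subject of this point.

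**The concern.** Patients are allocated 1:1 at random, and the first craving score comes before stimulation. Its expected arm difference is therefore known to be zero. The five-level interaction leaves that difference free, so it compares the later arm differences with a noisy estimate of a known quantity. With 16 to 17 patients per arm, that noise is not small.

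The noise is already in the test's error term, so this is a loss of precision and not a bias. What is at stake is power in a small trial whose authors expected dropout to be very common. The baseline score that could reduce the noise is already being collected.

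**Working it through.** **1. Reproduce the planned N, and confirm that baseline is an outcome level.** Inputs from the Statistical Analysis section: partial eta-squared 0.10384, SPSS convention, alpha 0.05, two arms. With m levels and sphericity:

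- f² = 0.10384/(1 − 0.10384) = 0.11587
- λ = f² (N − 2)(m − 1), df = (m − 1) and (N − 2)(m − 1)

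| m | N | λ | Power |
|---|---|---|---|
| 5 | 29 | 12.51 | 80.2% |
| 5 | 30 | 12.98 | 81.8% |
| 5 | 33 | 14.37 | 86.2% |
| 4 | 30 | 9.73 | 72.6% |
| 4 | 35 | 11.47 | 80.5% |

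Five levels give a minimum of 29, or 30 in equal arms, which is the stated figure. Four levels would need 35, or 36 in equal arms. The stated N therefore fits only if the pre-stimulation score is one of the outcome levels.

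**2. Compare noncentralities.** Assume compound symmetry with between-visit correlation ρ, and let d be the arm differences at the four later visits (baseline difference zero). Up to a common factor:

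- planned interaction: A/(1 − ρ), with A = Σd² − (Σd)²/5
- baseline-adjusted joint 4-df test: B/(1 − ρ), with B = Σd² − ρ(Σd)²/(1 + 4ρ)
- difference: (B − A)/(1 − ρ) = (Σd)²/[5(1 + 4ρ)], which is never negative and is zero only if the later arm differences sum to zero

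At ρ = 0.5:

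- Sustained effect, d = (1, 1, 1, 1): A = 4 − 16/5 = 0.800; B = 4 − 0.5×16/3 = 1.333; ratio 1.667.
- Linear build-up, d = (0.25, 0.5, 0.75, 1): A = 1.875 − 6.25/5 = 0.625; B = 1.875 − 0.5×6.25/3 = 0.833; ratio 1.333.
- Last visit only, d = (0, 0, 0, 1): A = 1 − 1/5 = 0.800; B = 1 − 0.5/3 = 0.833; ratio 1.042.

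**3. Convert to power.** For each profile and ρ, the effect is scaled so that the planned test has exactly the noncentrality in step 1. The adjusted noncentrality is that value × B/A × (N − 4)/(N − 3), where the last factor pays for estimating the baseline slope. Denominator df are taken as 3(N − 3). Example at N = 33, ρ = 0.5, sustained: 14.37 × 1.667 × 29/30 = 23.15 on 4 and 90 df, giving 97.7%.

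Power at N = 33, against 86.2% as planned:

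| ρ | Sustained | Build-up | Last visit only |
|---|---|---|---|
| 0.3 | 99.7% | 97.5% | 87.2% |
| 0.5 | 97.7% | 93.7% | 85.9% |
| 0.7 | 93.4% | 89.7% | 85.0% |
| 0.8 | 90.6% | 87.8% | 84.7% |

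At N = 30 and ρ = 0.5 the figures are 96.1% (sustained) and 90.6% (build-up), against 81.8% as planned.

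**4. Sensitivity to the covariance model.** A simulation at N = 33 (4,000 runs) with a fully unstructured multivariate ANCOVA gave 96% (sustained) and 91% (build-up) at ρ = 0.5, against about 87% for the planned ANOVA. At ρ = 0.8 it gave 86% and 82%, so no gain.

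**5. Type I error.** In simulation at N = 33, the compound-symmetry joint test rejected 4.6–5.6% of null trials under compound symmetry. Under AR(1) data it rejected 5.6–7.4%, against 5.4–8.2% for the planned ANOVA without a sphericity correction.

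**6. The tested term must change too.** If baseline is dropped from the outcomes and only visit x condition over the four later visits is tested, power at N = 30 falls to about 5% for a constant effect and 53% for a linear build-up. Those effects are scaled to give the planned test 81.8%.

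**The case against.** The strongest reply is that nothing here is an error. Under its own model the planned test holds its type I rate, it reaches the stated 80%, and the sample size and test agree on the number of levels. All of that stands, so this is a point about efficiency.

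Second, the documents give neither the between-visit correlation nor an effect profile. That also stands. A larger noncentrality does not guarantee more power once the slope and degrees of freedom are paid for, as the last-visit column shows. The introduction says, however, that the earlier study found craving reduced both during and after treatment. That fits a sustained or building effect better than one confined to the last visit.

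Third, the gain relies on a compound-symmetry type of covariance, and type I error drifts upward under AR(1). The planned ANOVA makes the same assumption and drifts similarly. A Greenhouse-Geisser correction would repair the ANOVA, but the plan states none.

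Fourth, two sham patients were excluded after randomisation (Participants section). If they are left out of the analysis, equal expected baselines are no longer strictly guaranteed. This qualifies the argument without removing it.

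Fifth, recruitment ended in April 2018, the document is dated October 2018, and it already reports normality results for the craving scores. Changing the primary test at that stage carries a credibility cost. This affects how the change is labelled.

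**Conclusion.** The concern holds as a weakness in efficiency, not in validity. The plan puts a score that treatment cannot affect among the outcomes of its primary test and makes no other use of it there. Under compound symmetry at N = 33, adjusting for it raises power from 86% to about 98% (sustained) or 94% (build-up) at ρ = 0.5, and to 91% or 88% at ρ = 0.8. For a build-up the gain is under 5 points once ρ reaches 0.7. For a last-visit-only effect it runs from about +1 point at ρ = 0.3 to −1.5 points at ρ = 0.8. With an unstructured covariance the gain largely disappears at ρ of about 0.7 or more. The direction is secure for effects that persist over several visits. The size depends on an assumed correlation, profile and covariance structure, so confidence in it is medium. The change should be made.

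**What to change.** Take the four later OCCS scores (three during stimulation, one after) as outcomes and the pre-stimulation OCCS as a covariate. Fit a mixed model with visit, condition, visit x condition and baseline OCCS, with the compound-symmetry type of covariance that the ANOVA implies, stated in advance. The primary test is condition and visit x condition jointly, on 4 df. An equivalent is to keep all five scores and constrain the arm means to be equal at the pre-stimulation visit. Visit x condition alone must not be the test once baseline leaves the outcomes. The five-level ANOVA can remain as a supportive analysis.

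The SAP should state whether treatment codes or results were known when the change was made. If they were, the adjusted model should be labelled post hoc and reported beside the planned ANOVA.

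The cost is SAP wording and one SPSS MIXED run on data already collected, plus one degree of freedom for the baseline slope and an assumption that the relation to baseline is linear. No extra patients or visits are needed.
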